4.2 STUDY ENDPOINTS

4.2.1 PRIMARY ENDPOINT

Overall response rate of immunocompromised patients with unresectable locally recurrent and/or metastatic cutaneous SCCHN.

4.2.2 SECONDARY ENDPOINTS

1. Progression-free survival
2. Overall survival
3. Acute and late immune-related and non-immune-related toxicities

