- Patients with grade ≥ 2 uveitis. Patients with grade 2 uveitis will generally be discontinued from study treatment, unless there is resolution to grade ≤ 1 AND discussion with and approval by the site principal investigators. All patients with grade ≥ 3 uveitis will be permanently discontinued from study treatment.

After other AEs, resumption of treatment may be at the initial dose level. A patient who does not

tolerate Cemiplimab-rwlc will be removed from the study. Refer to [Appendix 1](#) for additional management guidelines for immune-related toxicities.

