7.8 RESCUE MEDICATIONS, TREATMENTS, AND PROCEDURES

Immuno-oncology agents are associated with AEs that can differ in severity and duration than AEs caused by other therapeutic classes. Cemiplimab-rwlc is considered an immune-oncology agent in this protocol. Early recognition and management of AEs associated with immuno-oncology agents may mitigate severe toxicity. Management Algorithms have been developed to assist investigators in assessing and managing the following groups of AEs:

- Gastrointestinal
- Renal
- Pulmonary
- Hepatic
- Endocrinopathy
- Skin
- Neurological

The above algorithms can be found in [Appendix 1](#)

Hypersensitivity infusion reactions should be reported to the site principal investigator and Regeneron Pharmaceuticals, Inc. within 24 hours of the event regardless of grade. The following AE terms constitute hypersensitivity infusion reactions:

- Allergic reaction
- Anaphylaxis
- Cytokine release syndrome
- Serum sickness
- Infusion reactions
- Infusion-like reactions

Management of infusion reactions.

Infusion reaction treatment guidelines are summarized in Table 4 below. Institutional standards for infusion reactions may be followed if the treating physician deems them acceptable for this protocol.

Table 4. Management of infusion reaction

Grade 1 Mild reaction	Increase monitoring of vital signs as medically indicated until the patient is deemed medically stable in the opinion of the investigator	None

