8.1.1 DEFINITION OF ADVERSE EVENTS (AE)

An adverse event (AE) is defined as any untoward medical occurrence, including an exacerbation of a pre-existing condition, in a patient in a clinical investigation who received a pharmaceutical product. The event does not necessarily have to have a causal relation with this treatment. Grade 1 toxicities and lab abnormalities not deemed clinically significant will not be collected.

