8.2.2 RELATIONSHIP TO STUDY AGENT

For all collected AEs, the clinician who examines and evaluates the participant will determine the AE's causality based on temporal relationship and his/her clinical judgment. The degree of certainty about causality will be graded using the categories below.

Related – The AE is known to occur with the study agent, there is a reasonable possibility that the study agent caused the AE, or there is a temporal relationship between the study agent and event. Reasonable possibility means that there is evidence to suggest a causal relationship between the study agent and the AE.

Not Related – There is not a reasonable possibility that the administration of the study agent caused the event, there is no temporal relationship between the study agent and event onset, or an alternate

etiology has been established.

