8.3 TIME PERIOD AND FREQUENCY FOR EVENT ASSESSMENT AND FOLLOW-UP

The study participants will be monitored closely throughout the study for occurrence of AE or SAE. The patients will be educated regarding most common AEs and SAEs and will be encouraged to report promptly.

If AEs and SAEs occur, information to be collected includes event description, time of onset, clinician's assessment of severity, relationship to study product, and time of resolution/stabilization of event. All AEs occurring during the study will be documented appropriately, regardless of relationship. All AEs will be followed to adequate resolution.

Any medical condition that is present at the time that the participant is screened will be considered as baseline and not reported as an AE. However, if the study participant's condition deteriorates at any time during the study, it will be recorded as an AE. Unanticipated problems will be recorded in the data collection system throughout the study.

Events will be followed for outcome information until resolution or stabilization is achieved.

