8.4 REPORTING PROCEDURES

8.4.1 ADVERSE EVENT REPORTING

All AEs occurring prior to initiation of Cemiplimab-rwlc therapy do not need to be reported.

All AEs occurring after first administration of Cemiplimab-rwlc therapy and 30 days after last administration of Cemiplimab-rwlc will be considered as on treatment. All AEs will be collected and graded according to CTCAE v5.0, with the exception of Grade 1 laboratory abnormalities which will not be collected. All Grade 2 and above toxicities will be collected and documented by the investigator, but only Grade 3 toxicities deemed possibly, probably or definitely related to the study treatment will be reported on the appropriate CRFs/SAE reporting forms. Only SAEs will be reported to the PI and Regeneron Pharmaceuticals, Inc. All AEs, including those persisting after end of study treatment must be followed up until they have resolved or have been sufficiently characterized or the principal investigator decides to not further pursue them.

Serious and non-serious AEs occurring later than 30 days after last administration of trial drugs will only be reported in case they are considered drug-related or trial (procedure) related.

Deaths (unless they are considered drug-related or trial related) will not be reported as SAE when

they occur later than 30 days after last administration of the trial.

Serious and non-serious AEs occurring after the subjects initiate subsequent treatment will only be collected if deemed related to cemiplimab-rwlc.

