8.4.4 EVENTS OF SPECIAL INTEREST

Not Applicable.

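### The immune-related/non-immune-related toxicity endpoint has no prespecified classification or analysis; separately, the adverse event collection and reporting rules contradict each other.

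*Combined protocol and SAP*

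**What the plan says.** **The endpoint and what supports it.** Section 4.2.2, like the study summary, lists "Acute and late immune-related and non-immune-related toxicities" as the third secondary endpoint. The sections that should feed it are these:

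- 8.2.2 says of causality that "The degree of certainty about causality will be graded using the categories below". The categories are Related and Not Related to the study agent.
- 8.3 lists the event description, onset, severity, "relationship to study product, and time of resolution/stabilization of event".
- The entry under "8.4.4 EVENTS OF SPECIAL INTEREST" is Not Applicable.
- 10.4.4 promises tables and listings of exposure, adverse events, laboratory data, vital signs and performance status. It mentions neither the immune-related nor the acute/late split.
- Appendix 1 groups event terms by organ. Section 6.1.8 refers to it for "additional management guidelines for immune-related toxicities", not as a classification for analysis.

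**Collection and reporting.** Section 7.8 states: "Hypersensitivity infusion reactions should be reported to the site principal investigator and Regeneron Pharmaceuticals, Inc. within 24 hours of the event regardless of grade". Table 4 in that section has a Grade 1 row. Section 8.4.1 states: "Only SAEs will be reported to the PI and Regeneron Pharmaceuticals, Inc". Section 8.1.1 states: "Grade 1 toxicities and lab abnormalities not deemed clinically significant will not be collected". Section 8.4.1, however, excludes only Grade 1 laboratory abnormalities from collection and has Grade 2 and above documented by the investigator. It then limits entry on the CRF/SAE forms to Grade 3 toxicities judged possibly, probably or definitely related. Section 8.1 has all adverse events entered in the charts and CRFs.

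**The concern.** Section 2.1 says that the safety of the drug in this population is unknown, so the toxicity endpoint carries much of the trial's purpose. Eligibility makes attribution difficult. Section 5.1 admits active blood cancers, transaminases up to 5 times the upper limit of normal, platelets from 50 and neutrophils from 1.0 (both x 10^9/L), and 5.2 allows maintenance therapy for the blood cancer. A cytopenia, rash, diarrhea, hepatitis or pneumonitis in such a patient may come from the disease, its treatment, an infection or immune activation. The event term often cannot tell these apart. The judgement is best recorded when the event occurs; later, the result depends on the list that the analyst picks.

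The second defect concerns which events reach the database and the supplier. Six sites working from sections that disagree could capture different grades, and an infusion reaction that 7.8 wants reported could go unreported by a site that follows 8.4.1.

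**Working it through.** The plan gives no figure for this endpoint, so the check is mainly a comparison of sections. The only design calculation (10.5: 27 patients, null rate 0.15, difference 0.18, so 0.33 under the alternative) reproduces. With success declared at 7 or more responses of 27, the exact binomial gives alpha 0.0986 and power 0.838. This point does not depend on it.

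**Step 1: can the split be traced from endpoint to table?**

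| Needed | Where it would stand | What is there |
|---|---|---|
| Definition of immune-related | 8.2 or 8.4.4 | None; 8.4.4 not applicable |
| Attribution recorded per event | 8.2.2, 8.3 | Drug relationship only |
| Acute/late cut-point | 4.2.2, 8.4.1, 10.4.4 | None; 8.4.1 gives a 30-day on-treatment window, 7.3.5 gives late-toxicity visits 6 and 12 months after the end-of-treatment visit |
| Planned table | 10.4.4 | No split |

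**Step 2: could an existing list replace the attribution?** The candidates differ. Section 2.3.1 names encephalitis and mucositis among potential immune-related effects; Appendix 1, as far as its table can be read, has no row for either. Section 7.8 says the algorithms cover neurological events, and no such row is legible. For pruritus and rash, Appendix 1 applies only where the event is considered immune related, and that judgement is not among the 8.3 items.

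**Step 3: how much could the choice matter?** Let m be the number of patients whose classification depends on the list. The immune-related rate can then move by up to m/27. The documents give no value for m, so these are assumptions:

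- m = 1: 1/27 = 3.7 percentage points
- m = 3: 3/27 = 11.1 percentage points
- m = 9: 9/27 = 33.3 percentage points

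These are outer limits, not estimates. Drug-relatedness and recorded steroid use would narrow them.

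**Step 4: follow non-serious infusion reactions through the rules.**

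| Event | To supplier, 7.8 | To supplier, 8.4.1 | Collected, 8.1.1 | Collected, 8.4.1 | On CRF, 8.1 | On CRF/SAE forms, 8.4.1 read literally |
|---|---|---|---|---|---|---|
| Grade 1 | Yes | No | No (or unclear) | Yes | Yes | No |
| Grade 2, related | Yes | No | Yes | Yes | Yes | No |
| Grade 3, related | Yes | No | Yes | Yes | Yes | Yes |

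The two supplier columns disagree in every row. The two collection columns disagree at Grade 1. The two form columns disagree at Grades 1 and 2. The literal 8.4.1 wording would also leave out unrelated events and non-serious Grade 4 events. Its possibly/probably/definitely scale does not match the two categories in 8.2.2.

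**The case against.** A reader might infer more than the documents support, in four ways.

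- **That the endpoint cannot be produced.** It can be, after a fashion. Appendix 1 and 2.3.1 supply terms, 8.2.2 supplies relatedness, and concomitant prescription medications go on the CRF. Sections 7.4 and 7.6 allow oral or intravenous corticosteroids above 10 mg prednisone equivalent daily for immunological but not for non-immunological toxicities, so investigators already draw the line when such doses are considered. A split could be derived from these. What is missing is a rule fixed in advance.
- **That no immune-related classification is collected.** Section 8.3 introduces its items with the word includes, so the list may not be exhaustive. The CRF is not among the documents and may carry a field. Even so, the protocol would still lack a definition and an analysis.
- **That Section 8 drops infusion reactions.** It does not plainly do so. Section 8.4.1 collects Grade 2 and above and, by its own exclusion, Grade 1 non-laboratory events too. In 8.1.1, the qualifier about clinical significance may govern Grade 1 toxicities as well as laboratory findings. Section 7.8 can be read as a specific exception to a general rule. It also names the site principal investigator, whereas 8.4.1 names the PI, so the clear reporting conflict is the one about the supplier.
- **That the reporting conflict prevents the split.** It does not. Expedited reporting of infusion reactions has no bearing on how events are labelled.

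All of this limits the finding without removing it. The split is still not prespecified, and sites should not have to work out for themselves which section overrides which.

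**Conclusion.** Two separate defects stand; both should be corrected, and neither touches the primary analysis.

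1. The acute/late and immune-related/non-immune-related split in 4.2.2 has no definition, listed attribution, cut-point or planned table. Any version produced would rest on a list chosen after the fact, at 3.7 percentage points per reclassified patient. This assumes that the protocol text governs, because the CRF cannot be seen. How many patients would be affected is unknown.
2. Sections 7.8, 8.1, 8.1.1 and 8.4.1 disagree on which events are collected, which go on the CRF and which go to the supplier. The CRF conflict is the most consequential: read literally, 8.4.1 would leave Grade 2 events out of the safety data. This rests on the wording alone; sites may in practice follow 8.1.

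**What to change.** - **8.3 and the adverse event CRF:** add an investigator field, immune-related yes/no, with a short definition, completed at the time of the event for every collected adverse event. No extra steroid or hormone field is needed, because that use can be taken from the concomitant-medication CRF.
- **10.4.4:** add a table of immune-related and non-immune-related toxicities by acute and late, with the cut-point stated. The 30-day on-treatment window in 8.4.1 is one candidate, to be labelled as a choice because 8.4.1 does not call it acute. If it is used, note under the table that 8.4.1 reports later events only when they are considered drug- or trial-related, so the acute and late columns are collected under different rules.
- **7.8, 8.1, 8.1.1 and 8.4.1:** reconcile these so that the infusion reactions in 7.8 are an explicit exception, and the grades entered on the CRF are stated once. Without this, the new field might be completed only for related Grade 3 events. Use one causality scale in 8.2.2 and 8.4.1.

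The cost is one CRF field, one table and a few sentences. No treatment or visit changes.

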4.2.3 EXPLORATORY ENDPOINTS

1. Predictive biomarkers of Cemiplimab-rwlc response in CSCC.
2. Overall response rate of underlying CLL in the CLL subset.

5 STUDY ENROLLMENT AND WITHDRAWAL

5.1 PARTICIPANT INCLUSION CRITERIA

1. Histologically confirmed diagnosis of invasive CSCC.

Notes: Patients with mixed histologies (eg, sarcomatoid, adenosquamous) generally will not be eligible. Patients with mixed histology in which the predominant histology is invasive CSCC (with only a minimal component of mixed histology) may be eligible, after communication with

and approval from the each site principal investigator.

2. Immunocompromised patients with invasive CSCC. Immunocompromised patients are defined as:
 - a. History of HIV with CD4 counts ≥ 200 and no AIDS-defining illnesses.
 - b. History of treated or active hematologic malignancies including lymphoma, Hodgkin's disease, chronic lymphocytic leukemia, chronic myeloid leukemia, multiple myeloma, and myeloproliferative neoplasm.
3. At least 1 lesion that is measurable by study criteria by RECIST 1.1. Externally visible cutaneous SCC target lesion(s) greater than >10 mm, bi-dimensional measurements of the external lesion(s) with a color photograph may be used as target lesions.
4. Eastern Cooperative Oncology Group (ECOG) performance status 0-2.
5. ≥ 18 years old.
6. Hepatic function:
 - a. Total bilirubin $\leq 3.0 \times$ upper limit of normal (ULN)
 - b. Transaminases $\leq 5.0 \times$ ULN
 - c. Alkaline phosphatase (ALP) $\leq 5.0 \times$ ULN
7. Renal function: Estimated creatinine clearance (CrCl) >30 mL/min.
8. Bone marrow function:
 - a. Hemoglobin ≥ 8.0 g/dL
 - b. Absolute neutrophil count (ANC) $\geq 1.0 \times 10^9/L$
 - c. Platelet count $\geq 50 \times 10^9/L$
9. Ability to provide signed informed consent.
10. Ability and willingness to comply with scheduled visits, treatment plans, laboratory tests, and other study-related procedure.
11. Anticipated life expectancy >12 weeks.
12. CSCC not amenable to surgery or radiation therapy such as unresectable tumors determined by surgeons, surgical morbidity unacceptable by the patients, inability to deliver radiation safely determined by radiation oncologists, or radiation related toxicities unacceptable by the patients.

Note: In lieu of individual consults performed during screening, it will suffice to document the contraindication of surgery and radiation therapy via a clinic note from the investigator indicating that an individualized benefit:risk assessment was performed by a multidisciplinary team (consisting of, at minimum, a radiation oncologist AND EITHER a medical oncologist with expertise in cutaneous malignancies OR a dermatologist, OR a head and neck surgeon) within 60 days prior to enrollment in the proposed study, and the radiation therapy was deemed to be contraindicated. This is not required for patients with distant metastatic disease.

5.2 PARTICIPANT EXCLUSION CRITERIA

1. Prior known allergy to Cemiplimab-rwlc.

2. Prior exposure to PD-1 or PD-L1 inhibitors.
3. Prior exposure to idelalisib.

Note: Patients who have previously been treated with idelalisib will be excluded from treatment with cemiplimab as a result of the safety findings for 3 patients with indolent lymphoma previously treated with idelalisib, a phosphatidylinositol 3-kinase (PI 3-K) inhibitor, in study R1979-ONC-1504. Following a single dose of cemiplimab monotherapy in each case, 2 patients experienced severe stomatitis and/or skin reactions. The third patient experienced myositis and myasthenia gravis after 2 doses of cemiplimab.

4. Immunocompromised patients due to the solid organ transplant, allogeneic bone marrow transplant, and/or autoimmune disease.
5. Untreated brain metastasis(es) that may be considered active.

Note: Patients with brain involvement of CSCC due to direct extension of invading tumor, rather than metastasis, may be allowed to enroll if they do not require greater than 10 mg prednisone daily. Patients with previously treated brain metastases may participate provided that the lesion(s) is (are) stable (without evidence of progression for at least 4 weeks on imaging obtained in the screening period), and there is no evidence of new or enlarging brain metastases, and the patient does not require any immunosuppressive doses of systemic corticosteroids for management of brain metastasis(es) within 4 weeks of first dose of Cemiplimab-rwlc.

6. Immunosuppressive corticosteroid doses (> 10 mg prednisone daily or equivalent for >5 consecutive days) within 4 weeks prior to the first dose of Cemiplimab-rwlc.

Note: Patients who require brief course of steroids (eg, as prophylaxis for imaging studies due to hypersensitivity to contrast agents) are not excluded.

7. Known active infection requiring therapy, including acute infection with hepatitis B virus (HBV) or hepatitis C virus (HCV). However, it is not required to test only to determine the eligibility for the trial. As an exception, known HIV infection is allowed.
8. History of pneumonitis within the last 5 years.
9. Grade ≥ 3 hypercalcemia at time of enrollment.
10. Patients on any systemic anticancer treatment (chemotherapy, targeted systemic therapy, photodynamic therapy), investigational or standard of care for CSCC within 28 days of the initial administration of Cemiplimab-rwlc are excluded.
11. Patients on any systemic anticancer treatment (chemotherapy, targeted systemic therapy, photodynamic therapy), investigational or standard of care for non-hematologic malignancy within 28 days of the initial administration of Cemiplimab-rwlc or planned to occur during the study period are excluded.

Note:

- a. Patients receiving bisphosphonates or denosumab are not excluded.
- b. Patients receiving maintenance or supportive therapies for their hematological malignancies are not excluded.

- c. If the patients have been disease free for ≥ 2 years, patients receiving adjuvant hormonal therapies for breast cancer, prostate cancer, or thyroid cancer are not excluded.
- 12. Patients who cannot discontinue the concurrent use of other chemopreventive agents such as 5-FU, capecitabine, Efudex, imiquimod, acitretin are not allowed.
- 13. Radiation therapy within 7 days of initial administration of Cemiplimab-rwlc or planned to occur during the study period.
- 14. Breast feeding.
- 15. Positive serum pregnancy test (a false positive pregnancy test, if demonstrated by serial measurements and negative ultrasound, will not be exclusionary)
- 16. Concurrent non-hematologic malignancy other than cutaneous SCC within 3 years of date of first planned dose of Cemiplimab-rwlc , except for tumors with negligible risk of metastasis or death, such as adequately treated basal cell carcinoma of the skin, carcinoma *in situ* of the cervix, or ductal carcinoma *in situ* of the breast, or low-risk early stage prostate adenocarcinoma (T1-T2a N0 M0 and Gleason score ≤ 6 and PSA ≤ 10 ng/mL) for which the management plan is active surveillance, or prostate adenocarcinoma with biochemical-only recurrence with documented PSA doubling time of > 12 months for which the management plan is active surveillance.
- 17. Any acute or chronic psychiatric problems that, in the opinion of the investigator, make the patient ineligible for participation.
- 18. Continued sexual activity in men or women of childbearing potential who are unwilling to practice highly effective contraception during the study and until 6 months after the last dose of study drug.

Note: Highly effective contraceptive measures include stable use of oral contraceptives such as combined estrogen and progestogen and progestogen only hormonal contraception or other prescription pharmaceutical contraceptives for 2 or more menstrual cycles prior to screening; intrauterine device (IUD); intrauterine hormone-releasing system (IUS); bilateral tubal ligation; vasectomy, and sexual abstinence.

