7.2 LABORATORY PROCEDURES/EVALUATIONS

7.2.1 CLINICAL LABORATORY EVALUATIONS

Table 1. Clinical laboratory tests

Category	Tests
Laboratory tests	CBC w/differential (hemoglobin, hematocrit, WBC with differential count, platelet count) CMP (Sodium, potassium, bicarbonate, chloride, BUN, creatinine, total bilirubin, ALT, AST). Magnesium INR (only as part of the screening assessment or if clinically indicated) Amylase, lipase Hepatitis testing for only research purposes will not be performed, but documented if the status is known. HIV CD4 count as a standard of care
Pregnancy test	Serum or urine β -hCG (for women of childbearing potential)
Thyroid panel	TSH and free T4

ALT= alanine aminotransferase, AST=aspartate aminotransferase, β -hCG = beta-human chorionic gonadotropin, BUN=blood urea nitrogen CBC=complete blood count, CMP=comprehensive metabolic panel, INR = International Normalized Ratio, TSH= thyroid stimulating hormone, T4 = thyroxine, WBC=white blood cells.

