7.4 CONCOMITANT MEDICATIONS, TREATMENTS, AND PROCEDURES

All concomitant prescription medications taken during study participation will be recorded on the case report forms (CRFs).

All additional local therapies for metastatic lesions (including, but not limited to EBRT, surgery, embolization, ethanol injections, etc.) will be recorded on CRFs.

- Steroid: Treatment with oral/IV corticosteroids (>10mg daily prednisone equivalent) is not allowed for non-immunological toxicities. Treatment with oral/IV corticosteroids (>10mg daily prednisone equivalent) for immunological toxicities is permitted as detailed in the dose modification sections.
- Use of corticosteroids (\leq 10 mg daily prednisone equivalents) is allowed. Inhaled or topical steroids and adrenal replacement doses $>$ 10 mg daily prednisone equivalents are permitted in the absence of active autoimmune disease.
- Palliative radiation therapy is allowed to non-target lesions at the discretion of the treating physician. As concurrent radiotherapy and Cemiplimab-rwlc have not been formally evaluated, in cases where palliative radiotherapy is required for a tumor lesion, then Cemiplimab-rwlc should be withheld for at least 1 week before, during, and 1 week after radiation. Subjects should be closely monitored for any potential toxicity during and after receiving radiotherapy.
- Surgical resection of new and non-target cutaneous lesions that are $<$ 10mm is allowed at the discretion of the treating physician. Surgical resection of target lesions is only permissible if all previously identified target lesions are rendered operable. For guidance on the impact on response assessment refer to the composite response criteria found in Appendix 2.

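### The HIV limit (CD4 count and AIDS-defining illness) binds only route 2a, so a patient with a blood cancer and HIV who fails it can still enter through route 2b

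*Combined protocol and SAP*

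**What the plan says.** Section 5.1, item 2 opens with "Immunocompromised patients are defined as" and lists two entries, with neither *and* nor *or* between them:

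- 2a: "History of HIV with CD4 counts ≥ 200 and no AIDS-defining illnesses".
- 2b: "History of treated or active hematologic malignancies including lymphoma", followed by further named blood cancers. No HIV, CD4, transplant or autoimmune condition is attached.

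Three items in Section 5.2 bear on the same patients:

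- Item 4 excludes "Immunocompromised patients due to the solid organ transplant, allogeneic bone marrow transplant, and/or autoimmune disease".
- Item 6 excludes "Immunosuppressive corticosteroid doses (> 10 mg prednisone daily or equivalent for >5 consecutive days) within 4 weeks prior to the first dose of Cemiplimab-rwlc". No exclusion names other immunosuppressive drugs as a class.
- Item 7 excludes known active infection needing therapy, then adds "As an exception, known HIV infection is allowed". No CD4 floor is given there.

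Table 1 in Section 7.2.1 lists "HIV CD4 count as a standard of care". Section 7.4 says that inhaled or topical steroids and adrenal replacement doses are "permitted in the absence of active autoimmune disease".

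**The concern.** The plan sets a limit on how advanced HIV may be, but makes it part of one entry route instead of a condition on every patient with HIV. Someone with two reasons to be immunocompromised therefore meets a looser HIV rule than someone with one. Nothing in the protocol says that this is intended.

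This is a single-arm study of 27 patients. Its response rate and toxicity results will be read as describing a defined immunocompromised population. If the HIV limit holds for some HIV-positive patients and not for others, that population is not the one a reader would take from item 2a, and patients whom the plan otherwise keeps out can be treated.

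Exclusion 4 raises a milder form of the same problem. It looks to the cause of immunocompromise, and the protocol has no rule for a patient with two possible causes.

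**Working it through.** No arithmetic decides this point, so the check is to run example patients through the text.

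**Step 1: are 2a and 2b alternatives?** If both were required, every participant would need HIV and a blood cancer together. Nothing in the title, objectives or population statement suggests that, and the exploratory objective treats chronic lymphocytic leukemia (CLL) as a subset. I read them as alternatives.

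**Step 2: the HIV limit.** All other criteria are assumed to be met.

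| Patient | 2a | 2b | Item 2 met? | Excluded by 5.2 on HIV grounds? | Result |
|---|---|---|---|---|---|
| HIV, CD4 at least 200, no AIDS-defining illness, no blood cancer | yes | no | yes | no (item 7 exception) | enters |
| HIV, CD4 below 200, no blood cancer | no | no | no | not reached | kept out |
| HIV, CD4 below 200, CLL | no | yes | yes | no (item 7 exception) | enters |
| HIV with an AIDS-defining illness, lymphoma | no | yes | yes | no (item 7 exception) | enters |

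Rows 2 and 3 differ only by the added CLL, and the added disease turns a refusal into an entry. Exclusion 4 does not list HIV, and exclusion 6 concerns corticosteroids only. Section 5.4.1 allows removal of a participant who is found to meet an exclusion criterion, but the HIV limit is not an exclusion criterion, so that clause does not supply it.

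**Step 3: exclusion 4.** An exclusion applies whichever inclusion route was used, so meeting 2b does not cancel it.

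- Blood cancer plus a kidney graft that makes the patient immunocompromised: excluded on the plain words.
- Allograft given to treat the blood cancer: the patient meets 2b and has had a transplant named in item 4. Whether the immunocompromise is due to the graft, the cancer or both is left to whoever assigns the cause.
- Blood cancer plus autoimmune disease that does not itself cause immunocompromise: the words of item 4 do not clearly reach this patient, and nothing says whether that is intended.

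**Step 4: effect on the design figures.** Section 10.5 gives n = 27, P0 = 0.15 and a difference of 0.18, so P1 = 0.15 + 0.18 = 0.33. With success declared at 7 or more responses, the exact binomial gives P(X ≥ 7 | 27, 0.15) = 0.0986 and P(X ≥ 7 | 27, 0.33) = 0.838. Both match the plan. Neither depends on how items 2, 4 and 7 are read.

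**The case against.** The best defence is that the gap is narrow. It needs a patient with both HIV and a blood cancer who also fails the HIV limit, and the protocol does not suggest that such patients are expected in number. Every subject is registered through one coordinating office, which reviews the checklist and supporting documents (Section 16.3), so sites do not decide alone. The protocol also gives no reason for the HIV limit or for exclusion 4. They may describe which kinds of immunocompromise are studied, in which case tying them to a cause or route is natural.

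Much of this stands. Central review reduces variation between sites over exclusion 4. It does not close the HIV gap, because a reviewer who applies the criteria as written would confirm the patient in the third row of the table. If the limit is meant to shape the population and not to protect patients, the text still gives two answers for the same HIV status.

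Two stronger readings are tempting, and the documents do not support them:

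- A reader might infer that route 2b overrides exclusion 4, so that a CLL patient immunocompromised by a kidney graft could enter. Item 4 does not say that the listed cause must be the only one, and exclusions apply on top of inclusion. That patient is excluded.
- A reader might take the steroid clause in Section 7.4 as proof that patients with active autoimmune disease can be enrolled. It covers only inhaled, topical and adrenal-replacement steroids, and it could equally refer to autoimmune disease that arises on treatment.

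**Conclusion.** The HIV point holds. Followed exactly, the criteria admit a patient with a hematologic malignancy and HIV who fails the plan's own HIV limit. The conclusion rests on reading 2a and 2b as alternatives, which is the only workable reading.

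The point on exclusion 4 holds only as an ambiguity about cause. It concerns two groups: patients allografted for a blood cancer, and blood-cancer patients whose autoimmune disease does not itself cause immunocompromise. The text neither clearly admits nor clearly excludes them.

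No number can be put on either point, because the documents give no expected mix of HIV, blood cancer, transplant and autoimmune disease. A reader might try to size the problem by one patient's share of 27, or by the halting rule in Section 8.5. The share is the same for any participant. The halting rule counts grade 3 events judged probably related in any patients, and nothing shows that these patients would supply them. Alpha, power and the primary test are unaffected.

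**What to change.** 1. Make the existing limit on CD4 count and AIDS-defining illness apply to every patient with known HIV, whichever of 2a or 2b is used. One way is to state it as an item in Section 5.2 and cross-refer to it from exclusion 7. If the sponsor means the limit to lapse under 2b, the protocol should say so and give the reason.
2. Reconcile item 2b, exclusion 4 and Section 7.4 so that the two unsettled groups each have one answer. Which answer is for the sponsor to decide. Rewriting item 4 to exclude any prior transplant or any autoimmune disease would change the study population, so it should not be treated as a mere clarification.

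The cost is an amendment to a few criteria and to the registration checklist. No new test is needed, since the CD4 count is already listed as standard of care. The downside of the first change is that a rare patient with both a blood cancer and HIV beyond the limit could not enter. The protocol does not define AIDS-defining illness, so the revised item should also say whether the blood cancer that qualifies a patient under 2b can itself count as one.
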